3. PROTOCOL SYNOPSIS

Title	Photodynamic therapy with Levulan® and blue light for the treatment of actinic cheilitis				
Protocol Number	1.0				
Study Medication	Levulan® Kerastick® containing 20% aminolevulinic acid HCL (ALA) (DUSA Pharmacueticals)				
Study Device	BLU-U Blue Light Photodynamic Therapy (PDT) Illuminator				
	Omnilux revive ^{2TM}				
Study Objectives	To evaluate the safety and efficacy of PDT with blue light and topical Levulan® in the treatment of actinic cheilitis				
Study Design	This is a single center, investigator initiated, nonrandomized, open-				
	label, proof of concept study of PDT with blue light and topical				
	Levulan® in the treatment of actinic cheilitis				
Inclusion Criteria	Must be able to understand and voluntarily sign an				
	informed consent form				
	Must be male or female ≥ 18 years of age at the time of				
	consent				
	Must be able to adhere to the study visit schedule and				
	other protocol requirements				
	Must have a diagnosis of actinic cheilitis by				
	histopathological evaluation of biopsy specimen or clinical				
	presentation				
Exclusion Criteria	Inability to provide voluntarily consent or mentally				
	incompetent				
	No active herpes labialis lesions				
	Subjects with any condition which places the subject at				
	unacceptable risk if he/she were to participate in the study,				
	or confounds the ability to interpret data from the study				
	Subjects with any other skin condition that might affect the				
	evaluation of the study disease				
	Pregnant or breastfeeding female subjects				

- Subjects who have used any investigational medication within one month prior to study entry
- Subjects who have been previously exposed to PDT and/or topical Levulan[®] therapy
- Subjects who have used local therapy (e.g. cryotherapy) or topical treatment (e.g. 5% fluorouracil) within three months of study entry
- Subjects who have used an oral photosensitizing drug (e.g. Declomycin[®]) within six months of study entry
- Subjects who are currently using photosensitizing agents (e.g. thiazides, tetracyclines, fluoroquinolones, phenothiazines, and sulfonamides) because of the risk of augmented photosensitivity
- Subjects who are frequently exposed to ultraviolet radiation (e.g. lifeguards, construction workers, frequent sunbed users, etc.)
- Subjects with a history of cutaneous photosensitization, porphyria, hypersensitivity to porphyrins, or photodermatosis
- Subjects with a known hypersensitivity to ALA
- Subjects who are immunocompromised

Study Procedures

The study will consist of a screening visit, up to three scheduled treatments, and two scheduled office visits. There can be a three-day window period for each scheduled visit in order to accommodate the subject's schedule and unforeseen scheduling conflicts.

 Visit 1 (Screening): Subjects can be screened for the study up to two weeks before Visit 2 (Baseline). During screening, the study will be reviewed, written informed consent obtained, and eligibility confirmed. If applicable, the washout from prohibited medications or treatments will be determined at this visit.

- 2. Visit 2 (Baseline): Following signed, written informed consent and confirmation of eligibility, all subjects will have their lips photographed. Medical history, dermatologic exam, urine pregnancy test (if applicable), review of concomitant medications, clinical evaluations, and tolerability assessments will be performed at this visit. Study medication application to clean skin will be followed by a ninety minute incubation period under occlusion. Subsequently, patients will be exposed to blue light therapy for 16 minutes and 40 seconds. Post-therapy assessments will be performed afterwards, as well as education on appropriate sun protection methods.
- 3. Visits 3-4: Subjects will return every six weeks for up to two additional treatments. Treatment will be discontinued once the patient has achieved clinical clearance. Tolerability assessments, study medication application, blue light therapy, post-therapy assessments, and photographs will be performed.
- 4. Visit 5-6 (End of Study): Subjects will return 12 and 24 weeks after the last treatment for clinical evaluations, tolerability assessments, and photographs.

Study Measurements

Primary efficacy will be assessed by the investigator for the following:

- Clearance will be estimated clinically as minimal (0%-25%), mild (26%-50%), moderate (51%-75%), good (76%-99%), or complete (100%).
- Results will also be evaluated by comparing photographs before and immediately after treatments, and 12 and 24 weeks after the last treatment.

Secondary endpoints will include the following:

 Subject reported pain during and after blue light illumination using a Visual Analogue Scale (VAS) from 0 (no pain) to 10 (worst pain imaginable).

	Percent of patients with adverse events.				
	Safety will be assessed by the investigator as follows:				
	 Local Skin Reactions: Assessment of swelling, 				
	vesiculation/pustulation, erosion/ulceration, erythema,				
	flaking/scaling, and crusting using a five-point ordinal scale				
	(0: none to 4: severe) will be conducted after each				
	treatment visit. The presence or absence of				
	hyperpigmentation in the treatment area will also be				
	documented after each treatment visit.				
	Subjects will be asked to rate their pain using a VAS both				
	during and after blue light treatment.				
	PDT Reactions: Other than those specified under local skin				
	reactions.				
	Adverse Events: Evaluation of any reported local or				
	systemic events outside the treatment area and other than				
	those specified under local skin reactions.				
Study Endpoints	Primary Endpoints:				
	Clearance will be estimated as a percentage improvement				
	from baseline.				
	Secondary Endpoints:				
	Tolerability of treatment and tabulation of reported local				
	and systemic adverse events.				
Study Duration	24 to 36 weeks				
Total Sample Size	20				

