4.0 SCHEDULE OF ASSESSMENTS

	Treatment Phase		Observational Follow-up Phase			
Visit Number	1 Screening	2 Baseline	3	4	5	6 End of Study/ Early Termination Visit
Week(s)	-2-0 weeks	day 0	6 weeks	12 weeks	24 weeks	36 weeks
Informed Consent	Х					
Medical History	Х					
Demographics	Х					
Inclusion/ Exclusion Criteria	х	х				
Concomitant Medications	Х	Х	х	х	Х	х
Physical Exam	Х	х				х
Treatments		х	Х	Х		
Physician Efficacy Assessments						
Comparison of photographs		х	х	х	х	х
Investigator Global Assessment		Х	х	х	Х	х
Subject Efficacy Assessments						
Subject Global Assessment of Improvement		х	х	х	х	х
DLQI		х	х	х	х	х
Physician Safety Assessments						

Page 11 of 32

		Treatment Phase				Observational Follow-up Phase	
Visit Number	1 Screening	2 Baseline	3	4	5	6 End of Study/ Early Termination Visit	
Week(s)	-2-0 weeks	day 0	6 weeks	12 weeks	24 weeks	36 weeks	
Swelling, Vesiculation, Erosion, Erythema, Flaking, Crusting		х	х	х	х	х	
Hyperpigmentatio n		х	х	х	х	х	
Adverse Events		х	х	х	х	х	
Pregnancy Testing ^d	х	х				х	
Subject Safety Assessments							
Redness, swelling, and dryness		х	х	х	х	Х	
Pain (VAS Scale)		х	х	х	х	Х	
Photographs		Х	х	Х	Х	Х	

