9.2.2 PRE & POST-TREATMENT SAFETY ASSESSMENTS

A study physician will complete post-treatment assessments based upon visual observation of *swelling, vesiculation/pustulation, erosion/ulceration, erythema, flaking/scaling,* and *crusting.* The assessment will be based upon the scaling system below:

Swelling	Grade 0: not present
	Grade 1: slight, lesion specific edema
	Grade 2: palpable edema extending beyond individual lesions

	Grade 3: confluent or visible edema
	Grade 4: marked swelling, very easily noticeable from a
	distance
Vesiculation/Pustulation	Grade 0: not present
	Grade 1: only vesicles
	Grade 2: <50% pustules with or without vesicles
	Grade 3: > 50%, but <75% pustules with or without vesicles
	Grade 4: >75% pustules with or without vesicles
Erosion/Ulceration	Grade 0: not present
	Grade 1: lesion specific erosion
	Grade 2: erosion extending beyond individual lesions
	Grade 3: erosion >50%
	Grade 4: black eschar or ulceration
Erythema	Grade 0: not present
	Grade 1: slightly pink <50%
	Grade 2: pink or light red >50%
	Grade 3: red 50-75%
	Grade 4: severe redness, >75%, very easily noticeable from a
	distance
Flaking/Scaling	Grade 0: not present
	Grade 1: isolated scale, specific to lesions
	Grade 2: scale <50%
	Grade 3: scale >50%, but <75%
	Grade 4: scale >75%, very easily noticeable from a distance
Crusting	Grade 0: not present
	Grade 1: isolated crusting
	Grade 2: crusting <50%
	Grade 3: crusting >50%
	Grade 4: crusting >75%, very easily noticeable from a distance

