9.3.4 TWO-DAY POST-TREATMENT TELEPHONE FOLLOW-UP VISIT

Patients will be asked to rate *redness, swelling,* and *dryness* on the scale below. The scales will be read to the patient over the phone.

Redness	Grade 0: None
	Grade 1: Minimal redness, only a little noticeable

	Grade 2: Mild redness, easily noticeable and involving less than 1/3 of the face
	Grade 3: Moderate redness, easily noticeable and involving between 1/3 and 2/3 of the face
	Grade 4: Severe redness, very easily noticeable from a distance, and involving over 2/3 of the face
Swelling	Grade 0: None
_	Grade 1: Minimal swelling, only a little noticeable
	Grade 2: Mild swelling, easily noticeable and involving less than 1/3
	of the face
	Grade 3: Moderate swelling, easily noticeable and involving
	between 1/3 and 2/3 of the face
	Grade 4: Severe swelling, very easily noticeable from a distance,
	and involving over 2/3 of the face
Dryness of Skin	Grade 0: None
	Grade 1: Minimal dry skin, only a little noticeable
	Grade 2: Mild dry skin, easily noticeable and involving less than
	1/3 of the face
	Grade 3: Moderate dry skin, easily noticeable and involving
	between 1/3 and 2/3 of the face
	Grade 4: Severe dry skin, very easily noticeable from a distance,
	and involving over 2/3 of the face

Additionally the subject will be asked the open-ended question, "Have you had any problems since leaving our office after your last appointment?" The study coordinator will then record each subject's response in the appropriate source document.

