10. ASSESSMENT OF ADVERSE EVENTS

Safety precautions, such as the use of highly experienced investigators, frequent office visits, and close monitoring of clinical and laboratory findings (pregnancy tests) have been implemented in the protocol and are specified in the Schedule of Assessments (see Section 4). All unexpected physical examination findings will be captured as Adverse Events (AEs) when deemed medically significant by the investigator. Potential events that are anticipated post-treatment include erythema and pain. Other, less frequent potential events associated with any dermatological PDT include bleeding, crusting, numbness, itching, blistering and dryness, all of which tend to be transient.

A qualified physician associated with the study will be available to assess clinical signs and symptoms that may be indicative of an AE. Any clinical sign or symptom that was not present at baseline and are not included in the expected side effect profile of PDT will be recorded as an AE. AEs may be reported spontaneously by the patient or elicited

through open (non-leading) questioning during each visit and up until the end of the period of observation (week 36; Visit 6).

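### The synopsis lists PDT Reactions as a safety measure but nothing schedules or rates it, and conflicting adverse event rules leave it unclear whether bleeding, numbness and itching of the treated lip reach any tabulated result

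*Combined protocol and SAP*

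**What the plan says.** **Synopsis (Section 3).** Study Measurements lists how the investigator will assess safety: local skin reactions, pain on a VAS, a category worded "PDT Reactions: Other than those specified under local skin" reactions, and adverse events. The adverse event line covers local or "systemic events outside the treatment area and other than" the listed local skin reactions. Study Measurements also names the percentage of patients with adverse events as a secondary endpoint. The secondary endpoint under Study Endpoints is "Tolerability of treatment and tabulation of reported local" and systemic adverse events.

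**Schedule (Section 4).** The physician safety rows are "Swelling, Vesiculation, Erosion, Erythema, Flaking, Crusting", hyperpigmentation, adverse events and pregnancy testing. The subject safety rows are "Redness, swelling, and dryness" and pain. No row is labelled PDT Reactions. Section 9 ties the timing of safety assessments in the treatment phase to this schedule.

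**Rating forms (Section 9).** Section 9.2.2 reads "A study physician will complete post-treatment assessments based upon visual observation of" six graded signs. Section 9.3.2 gives the pain VAS. Section 9.3.4 describes a telephone call two days after treatment, with scales for redness, swelling and dryness and the open question "Have you had any problems since leaving our office after your last appointment". The answer goes to a source document.

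**Adverse events (Section 10).** The opening text names erythema and pain as anticipated, and "bleeding, crusting, numbness, itching, blistering and dryness" as less frequent and generally transient. It then limits adverse events to new signs or symptoms that lie outside the expected PDT side effect profile. Section 10.2.1 defines an adverse event as any untoward medical occurrence, whatever its cause.

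**The concern.** Safety is half of the single study objective, and tolerability is a secondary endpoint. Section 5 also suggests that PDT, if efficacious, could be among the safest options for this condition. A reaction that the protocol itself expects should therefore have a definite route into a results table: a rating scale, a PDT Reactions listing or the adverse event table.

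For three expected reactions no route is clear. The residual category that appears meant for them has no collection point. The adverse event route is open or closed depending on which passage the investigator follows. Two investigators could record the same numb or itchy lip differently, and both would be following the protocol. Reactions that are transient and not recorded near the time of treatment cannot be recovered at analysis. Numbness and itch would not show in the photographs either.

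**Working it through.** The documents give no figure to reproduce on this point. The check is a count, followed by a comparison of passages.

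**Step 1. Match each anticipated reaction to a dedicated safety rating.** Section 10 names 2 common and 6 less frequent reactions: 2 + 6 = 8.

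| Reaction (Section 10) | Dedicated safety rating |
|---|---|
| Erythema | Physician scale, 9.2.2 |
| Pain | VAS, 9.3.2 |
| Crusting | Physician scale, 9.2.2 |
| Blistering | Physician scale, 9.2.2 (taken as vesiculation) |
| Dryness | Two-day call, 9.3.4 |
| Bleeding | None |
| Numbness | None |
| Itching | None |

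Rated: 5 of 8. Not rated: 8 − 5 = 3, and 3/8 = 37.5%. The physician form rests on visual observation, so it could not detect numbness or itch. Bleeding is visible but is not among the six signs.

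**Step 2. Does the adverse event count pick up these three when they occur on the treated lip?**

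| Passage | Rule | Of the 3, eligible as adverse events |
|---|---|---|
| Section 10, opening text | Only signs outside the expected PDT profile | 0 |
| Synopsis, adverse event line | Events outside the treatment area | 0 |
| Section 10.2.1 | Any untoward occurrence | 3 |
| Synopsis, Study Endpoints | Tabulate reported local and systemic events | 3, if reported |

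The answer runs from none to all three, and the documents do not say which passage governs. The exception for expected side effects in Section 10.2.1 concerns worsening of an established condition, so it does not settle the matter.

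**Step 3. Can the DLQI stand in for itch?** Item 1 (Section 9.3.3) combines itch with soreness, pain and stinging over the past week, and the questionnaire is completed before any other procedure at the visit. The baseline DLQI therefore precedes the first treatment. The next visit is nominally 6 × 7 = 42 days later, so the recall period covers days 35 to 42 after treatment. If the three-day windows at both visits shortened the gap as far as possible, the interval would be 42 − 6 = 36 days and recall would begin at day 29. Section 7.5 says local skin reactions typically resolve in one to two weeks, that is by day 14. Recall then starts at least 29 − 14 = 15 days too late. The schedule also lists the DLQI under efficacy. Counting item 1 all the same, 2 of 8 reactions (25%) appear on no structured form.

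**Step 4. Can the two-day call stand in?** Its timing is good, and the open question could elicit all three reactions. No grading, coding or tabulation of the answer is stated, and an unprompted answer does not separate a reaction that was absent from one that was not mentioned.

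**The case against.** The strongest reply is that no form in the text does not mean no collection. The synopsis says that the investigator will assess PDT Reactions, and a residual category can be recorded as free text. Adverse events have a schedule row at Visits 2 to 6, Section 10 provides for open questioning at each visit, and Section 10.2.1 is broad enough to include all three reactions. The case report form is not part of the documents, and a figure in Section 9.3 is not shown, so nobody can say that no form exists anywhere. In a 20-subject open-label proof-of-concept study, prompted items may also look like a matter of preference.

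Much of this stands. A reader might infer that bleeding, numbness and itching fall outside every tolerability result, so that a report would read as if they had not occurred. The documents do not support that. Section 10.2.1, the promised tabulation of local events, the questioning at visits and the recorded call answer each leave a way in.

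The reply does not remove the conflict. The opening of Section 10 and the synopsis adverse event line each give an investigator explicit grounds not to record an expected reaction on the treated lip as an adverse event. If those rules are followed, nothing else scheduled is dedicated to these three reactions.

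**Conclusion.** The point holds as a gap in specification combined with an internal contradiction. A named safety measure has no schedule row and no scale or items in the protocol text. Three of the eight anticipated reactions have no dedicated safety rating (two of eight are on no structured form if DLQI item 1 is credited for itch). Under the opening of Section 10 and the synopsis adverse event line they would not enter the adverse event count; under Section 10.2.1 they would. Whether they reach any tabulated result is therefore unclear.

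The number of subjects affected cannot be derived. The documents give no incidence for these reactions, and any count would also need an assumed share missed by visit questioning and the call.

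The count of three treats blistering as covered by the vesiculation scale and relies on the protocol text alone. A case report form with items for these reactions would close the collection gap but not the conflict over what counts as an adverse event. The change is worth making before enrolment, because analysis cannot repair what was not recorded.

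**What to change.** - Add a PDT Reactions row to Section 4 at each treatment visit and at the two-day call. The schedule has no column for the call, so add a column or a footnote.
- Under that row, collect bleeding, numbness and itching as yes/no items, with any yes graded mild, moderate or severe using the Section 10.2.3 definitions.
- Code the answers to the existing open question on the call into the same table, and tabulate by treatment number within the tolerability endpoint.
- Reconcile the adverse event wording in the synopsis, the opening of Section 10 and Section 10.2.1. State whether expected reactions in the treatment area count as adverse events, PDT Reactions or both, and ensure that each event is counted once in any total. Without this step the new row could produce double counting.

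**Cost.** Three more items on an existing form and call script, one more table, and an edit to three passages. No new visit or staff is needed. Prompted items will probably raise the reported frequency of these reactions, so the safety profile will look less favourable than with open questioning alone.

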4.0 SCHEDULE OF ASSESSMENTS

	Treatment Phase		Observational Follow-up Phase			
Visit Number	1 Screening	2 Baseline	3	4	5	6 End of Study/ Early Termination Visit
Week(s)	-2-0 weeks	day 0	6 weeks	12 weeks	24 weeks	36 weeks
Informed Consent	Х					
Medical History	Х					
Demographics	Х					
Inclusion/ Exclusion Criteria	х	х				
Concomitant Medications	Х	Х	х	х	Х	х
Physical Exam	Х	х				х
Treatments		х	Х	Х		
Physician Efficacy Assessments						
Comparison of photographs		х	х	х	х	х
Investigator Global Assessment		Х	х	х	Х	х
Subject Efficacy Assessments						
Subject Global Assessment of Improvement		х	х	х	х	х
DLQI		х	х	х	х	х
Physician Safety Assessments						

Page 11 of 32

		Treatment Phase				Observational Follow-up Phase	
Visit Number	1 Screening	2 Baseline	3	4	5	6 End of Study/ Early Termination Visit	
Week(s)	-2-0 weeks	day 0	6 weeks	12 weeks	24 weeks	36 weeks	
Swelling, Vesiculation, Erosion, Erythema, Flaking, Crusting		х	х	х	х	х	
Hyperpigmentatio n		х	х	х	х	х	
Adverse Events		х	х	х	х	х	
Pregnancy Testing ^d	х	х				х	
Subject Safety Assessments							
Redness, swelling, and dryness		х	х	х	х	Х	
Pain (VAS Scale)		х	х	х	х	Х	
Photographs		Х	х	Х	Х	Х	

5. INTRODUCTION & RATIONALE

Actinic cheilitis is a common precancerous malformation of the lower lip caused by UV radiation. Conventional therapies, such as cryotherapy, topical 5-fluorouracil, Imiquimod, chemical peels, electrodessication, laser ablation, and vermilionectomy are oftentimes successful in the majority of patients. However, these treatments may be expensive, time-consuming, associated with noncompliance, have a high recurrence rate, require local or general anesthesia, and offer risk of unaesthetic scars. There are also numerous adverse side effects associated with the aforementioned treatments; therefore, alternative treatments for the treatment of actinic cheilitis are essential.

In the literature, several reports have shown photodynamic therapy (PDT) to be efficacious in the treatment of actinic cheilitis. Of note, patients in these case reports/series received therapeutic benefit with relatively few PDT treatments, which were associated with minimal cutaneous side effects. PDT is based on the combined use of photosensitizers and photoradiation. Topically applied δ -aminolevulinic acid (ALA) is theorized to be taken up by premalignant cells. Upon irradiation with a light source, photoactivated porphyrins produce singlet oxygen and other potent oxidizers, resulting in cell death. Unfortunately, controlled clinical trials assessing the efficacy of PDT for actinic cheilitis are lacking. As PDT does not appear to have any systemic side effects, if proven efficacious, PDT could be one of the safest treatment options for actinic cheilitis.

6. STUDY OBJECTIVE

To evaluate the safety and efficacy of PDT with blue light and topical Levulan® (aminolevulinic acid) in the treatment of actinic cheilitis.

6.1 HYPOTHESIS

The use of PDT with blue light and topical Levulan treatment will reduce the number of actinic cheilitis lesions.

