7.4 DURATION OF TREATMENT

After the screening visit, subjects will receive in-office treatments every six weeks for 12 weeks for up to a total of 3 treatments. Treatment will be discontinued once the patient has achieved clinical clearance. Each subject will then be followed for 24 weeks after the last treatment visit. In total, each subject will be part of the study for approximately 36 weeks.

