9.2 PHYSICIAN PERFORMED ASSESSMENTS

9.2.1 EFFICACY ASSESSMENTS

Primary efficacy will be assessed by the investigator for clearance from baseline (Visit 2) to the end of study (Visit 6; week 36). Clearance will be estimated clinically as minimal (0%-25%), mild (26%-50%), moderate (51%-75%), good (76%-99%), or complete (100%). Clinical photographs will also be taken at Visit 2 to 6. Care will be taken to avoid including any identifying landmarks, such as characteristic tattoos, birthmarks, etc.

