9.3.1 SUBJECT GLOBAL ASSESSMENT

The subject global assessment of improvement will be performed during every visit (except baseline) to assess the subject's impression of their overall improvement as compared to baseline. The subject global assessment scale is defined as follows:

Excellent improvement	My lip lesions are completely (100%) gone, except for possibly some residual color change
Marked improvement	My lip lesions are greatly (~75%) improved
Moderate improvement	My lip lesions are definitely (~50%) improved
Mild improvement	My lip lesions are somewhat (~25%) improved
No improvement	My lip lesions are not (0%) improved

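### Section 6.1 predicts fewer lesions, but no lesion count is planned, and the primary clearance scale neither names its unit, separates no change from slight benefit, nor has a level for worsening

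*Combined protocol and SAP*

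**What the plan says.** The hypothesis in Section 6.1 is about lesion number: treatment "will reduce the number of actinic cheilitis lesions".

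The efficacy measures are described differently:

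- **Section 9.2.1**, and the Study Measurements entry of the synopsis (Section 3), give five bands: "Clearance will be estimated clinically as minimal (0%-25%), mild (26%-50%), moderate (51%-75%), good (76%-99%), or complete (100" per cent).
- **The Study Endpoints entry of the synopsis** gives no bands: "Clearance will be estimated as a percentage improvement" from baseline.
- **Study Measurements** opens with "Primary efficacy will be assessed by the investigator for the following" and lists, beside the bands, a photographic element: "Results will also be evaluated by comparing photographs before and immediately after treatments, and 12 and 24 weeks after the last treatment".
- **Section 4.0** schedules a comparison of photographs and an Investigator Global Assessment at Visits 2 to 6. It has no row for a lesion count.
- **Section 9.3.1** gives subjects a five-level scale that refers to their lip lesions, from "My lip lesions are completely (100%) gone, except for possibly some residual color change" down to "My lip lesions are not (0%) improved".

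Section 7.4 also makes treatment depend on the same word: "Treatment will be discontinued once the patient has achieved clinical clearance".

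**The concern.** The hypothesis names one quantity and the primary measure may record another. Clearance could mean fewer lesions, a smaller affected area or milder disease, and a result of 'moderate' bears on Section 6.1 in different ways under each.

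The second problem concerns the scale itself. The study is nonrandomized and open-label, and the protocol describes no comparator group, so the investigator's rating carries the efficacy conclusion. If the lowest label is a form of clearance, a subject with no response, or whose lip has deteriorated, is reported as having cleared minimally. Section 5 describes the condition as precancerous, so readers will want to see deterioration in the efficacy results.

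**Working it through.** The plan states no figure to reproduce: 20 subjects are given in Section 7.2 without a test, power, effect size or responder cut-off, and Section 12.1 leaves the analysis to be worked out later. The check is therefore mainly a comparison of the relevant sections.

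**1. Is lesion number recorded anywhere?** The synopsis, the schedule (4.0), the visit procedures (7.3) and the physician efficacy assessments (9.2.1) contain no lesion count. The Investigator Global Assessment has no scale in the text of Section 9, and the plan does not say whether it is the clearance scale. No scoring rule is given for the photographs.

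**2. Which investigator bands would imply fewer lesions?**

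- If clearance means net lesion number, any value of 26% or more requires at least one lesion fewer. Mild, moderate, good and complete qualify: 4 of 5.
- If it means area or severity, values up to 99% can occur with every lesion still present. Only complete qualifies: 1 of 5.

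This follows from the definitions alone and does not measure any effect in this trial. It shows that the link to Section 6.1 depends on a unit that is not stated.

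**3. What can each scale express?**

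| State of the lip against baseline | Investigator band (9.2.1) | Subject level (9.3.1) |
|---|---|---|
| Worse | no level; lowest available is minimal | no level; lowest available is no improvement |
| Unchanged (0%) | minimal | no improvement |
| 20% better | minimal | mild (nearest anchor, about 25%) |
| Fully cleared (100%) | complete | excellent |

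Levels for worsening: 0 of 5 (investigator) and 0 of 5 (subject). Levels for no change alone: 0 of 5 and 1 of 5. The subject count rests on the text of 9.3.1; a figure in 9.3 is not available.

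**4. Does the unbanded endpoint help?** A recorded percentage would separate 0% from 20%. But Study Measurements and 9.2.1 supply only the bands, none of which starts below 0%. The case report form is not among the documents, so it is not known whether a raw percentage is captured.

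**5. Would worsening be captured as an adverse event?** Section 10.2.1 counts worsening of an established condition, apart from expected treatment effects. The safety entry in the synopsis describes adverse events as lying outside the treatment area. On the first, progression of the treated lip is an adverse event; on the second, it may not be.

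**6. Precision of the reporting proposed below.** Clopper-Pearson 95% intervals with n = 20, for illustrative counts and not forecasts:

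- 0/20 rated worse: lower limit 0, upper limit 1 − 0.025^(1/20) = 16.8%
- 2/20 rated worse: 1.2% to 31.7%
- 10/20 with complete clearance: 27.2% to 72.8%

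**The case against.** The strongest reply is that this is a 20-subject proof-of-concept study whose formal objective (Section 6) is general safety and efficacy. Coarse bands are a legitimate choice, no success rule depends on the lowest one, and the mismatch with a one-sentence hypothesis can be cured by rewording that sentence. Much of this stands, and it is why the point is not graded higher. It does not answer the lower end of the scale: even a proof-of-concept study needs to tell no effect from some effect.

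Four stronger readings are tempting, and the documents do not support them:

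- *Section 6.1 cannot be tested at all.* Photographs are taken at Visits 2 to 6 and their comparison is listed under primary efficacy, so a later count may be possible if lesions can be counted. If clearance means net number, most bands already bear on the hypothesis.
- *No change and slight benefit are inseparable whatever is recorded.* The unbanded wording in the synopsis leaves open that a raw percentage is captured.
- *Deterioration would be lost altogether.* Photographs might show it, and the adverse-event route may capture it; the percentage of patients with adverse events is a named secondary endpoint. Both routes are uncertain, and neither puts worsening on the efficacy scale.
- *Ratings will be unreliable within a subject.* Section 9 asks that the same investigator rate a given subject throughout, with a substitute only if that person has overlapping experience with the subject. This limits variation within a subject. It does not supply the missing unit or levels.

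**Conclusion.** The point holds as a cheap improvement of minor to moderate severity. Section 6.1 and the primary measure are not shown to concern the same quantity. The only investigator efficacy scale that the text defines has no level for no change alone and none for worsening, so an unchanged or progressing lip would be labelled minimal clearance.

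The size is structural. The documents give no lesion counts, areas or expected response rates from which to estimate how many of the 20 subjects would be affected. Complete clearance has a band of its own, although what is cleared still needs defining. The conclusion assumes that the case report form follows the bands in 9.2.1; if it captures a raw percentage, the merging of 0% with slight benefit falls away. The absence of a level for worsening would then depend on whether negative values are allowed.

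**What to change.** 1. Split the lowest investigator band into 'worse than baseline', 'none (0%)' and 'minimal (1%-25%)', rated against the Visit 2 photograph. Add a 'worse' level to the subject scale.
2. State what the clearance percentage refers to (lesion number, affected area or a named severity judgement) and restate Section 6.1 in terms of that endpoint. A lesion count is optional, and sensible only if lesions can be counted in all subjects.
3. Report the full distribution of levels out of 20, with unrated subjects in their own row. Give the proportion with complete clearance with an exact 95% confidence interval, as an estimate and not a test.
4. Say whether the Investigator Global Assessment is this scale, and either score the photograph comparison on the same levels or label it descriptive.
5. Reconcile the term 'clinical clearance' in the synopsis and Sections 7.3 and 7.4 with the scale, and reconcile the two descriptions of adverse events. No clinical rule is proposed here.

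The cost is minor wording and case report form changes. Efficacy is already rated at the scheduled visits, so no visit is added. Results may look slightly less favourable, because unchanged and worsened subjects would become visible.
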